#### **Joint circumference [mm]**

The joint circumference measurement is carried out by hand with a tape measure. This measurement method showed a high level of reliability. 5cm, 10cm, 15cm above the knee joint space, at the level of the knee joint space, 15cm below the knee joint space, above the lateral malleolus and above the scaphoid bone (Oesch 2007). Both sides are measured. The measurement moments take place preoperatively, on the 4th postoperative day and 6 weeks postoperatively.

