## 5. CLINICAL INVESTIGATION OUTCOMES

### 5.1 Primary Outcome

This study aims to investigate the effects of cryotherapy with intermittent dynamic compression with Game Ready during a hospital stay. The preoperative measurement is the baseline, the 4th postoperative day is the primary endpoint and the measurement 6 weeks postoperative is declared as follow-up. The following parameters are examined for this purpose:

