#### **Skin temperature [°C]**

Skin temperature is also recorded with the help of an infrared thermometer (Voltcraft IR800-20D, Conrad Electronic, Hirschau, Germany). Handheld infrared thermal devices have high measurement accuracy (due to contact-free measurement) and practical handling (Stoop et al. 2020). Skin temperature is measured at four locations of the knee: superolateral, superomedial, inferolateral, and inferomedial margin of the patella (Zeng et al. 2016). The subject is in a supine position during the measurements. Both sides are measured. The measurement moments take place preoperatively, on the 4th postoperative day and 6 weeks postoperatively.

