## **11. STATISTICAL METHODS**

### **11.1 Hypothesis**

Physical Function [AU]

H0: The use of cryotherapy with intermittent dynamic compression has no positive effect on the physical functions of patients after a total knee arthroplasty.

H1: The use of cryotherapy with intermittent dynamic compression has a positive effect on the physical functions of patients after a total knee arthroplasty.

Patient satisfaction [cm]

H0: The use of cryotherapy with intermittent dynamic compression has no positive effect on patient satisfaction of patients after a total knee arthroplasty.

H1: The use of cryotherapy with intermittent dynamic compression has a positive effect on patient satisfaction of patients after a total knee arthroplasty.

Joint circumference [mm]

H0: The joint circumference is not reduced by cryotherapy with intermittent dynamic compression compared to the control group during a hospital stay.

H1: The joint circumference is reduced by cryotherapy with intermittent dynamic compression compared to the control group during a hospital stay.

Skin temperature [C°]

H0: The skin temperature is not reduced by cryotherapy with intermittent dynamic compression compared to the control group during a hospital stay.

H1: The skin temperature is reduced by cryotherapy with intermittent dynamic compression compared to the control group during a hospital stay.

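### Joint circumference and skin temperature are each one primary outcome with one hypothesis, but the plan never says which leg, site or summary is analysed

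*Combined protocol and SAP*

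**What the plan says.** Section 5.1, repeated in 9.2.1, lists the circumference sites as "5cm, 10cm, 15cm above the knee joint space, at the level of the knee joint space, 15cm below the knee joint space", and continues "above the lateral malleolus and above the scaphoid bone (Oesch 2007). Both sides are measured". That makes seven sites per leg. For skin temperature it says "Skin temperature is measured at four locations of the knee: superolateral, superomedial, inferolateral, and inferomedial margin of the patella", and then "The subject is in a supine position during the measurements. Both sides are measured". That makes four sites per leg.

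The synopsis and section 4.2 list each of these as one of ten outcomes. Section 11.1 gives each one null and one alternative hypothesis: "H1: The joint circumference is reduced by cryotherapy with intermittent dynamic compression compared to the control group during a hospital stay" and "H1: The skin temperature is reduced by cryotherapy with intermittent dynamic compression compared to the control group during a hospital stay". Neither names a leg, a site or a summary. On timing, section 5.1 says "the 4th postoperative day is the primary endpoint".

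Section 11.4.2 describes a repeated-measures analysis, labelled MANOVA, with group and time as factors and p<0.05. It lists no dependent variables. Section 11.4.3 adds a secondary analysis in which the two sides of the body are compared. The synopsis names a Bonferroni correction without saying which tests it covers; section 11 does not mention it.

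**The concern.** An analyst cannot run 11.4.2 for these two outcomes without first choosing a leg and then a site, an average or some other summary. The plan leaves that choice open, so it can be made after the data are seen.

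If each operated-leg site is tested at 0.05, one significant site, possibly at the ankle or foot, could be reported as support for a hypothesis worded for joint circumference as a whole. A reader of the report could not tell whether that site was chosen in advance. This multiplicity lies inside a single listed outcome. Cutting the list of ten primary outcomes would not remove it if either of these two stayed on the list.

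**Working it through.** The documents give no familywise error rate or count of tests, so there is no figure of the plan's own to reproduce.

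**Inputs**
- Operated-leg sites, K: circumference 5 + 2 = 7; skin temperature 4 (section 5.1).
- Significance level: 0.05 (section 11.4.2). Sidedness is not stated, although the alternatives in 11.1 are directional. Two-sided tests are assumed first.
- Correlation between site-level test statistics, r: not in the documents. Assumed equal between all sites, with values 0, 0.5 and 0.8.

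**Formulas, with no device effect at any site**
- Independent sites, either direction: 1 − (1 − 0.05)^K. For K = 7, 1 − 0.95^7 = 0.302. For K = 4, 1 − 0.95^4 = 0.185.
- Independent sites, reductions only: 1 − (1 − 0.025)^K. For K = 7, 1 − 0.975^7 = 0.162. For K = 4, 1 − 0.975^4 = 0.096.
- Correlated sites, either direction: 1 − ∫ φ(u) [Φ((1.96 − √r·u)/√(1 − r)) − Φ((−1.96 − √r·u)/√(1 − r))]^K du. For reductions only, drop the second Φ term.

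**Chance of at least one false-positive site**

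| Outcome | Direction counted | r = 0 | r = 0.5 | r = 0.8 | Nominal |
|---|---|---|---|---|---|
| Circumference, 7 sites | either | 30.2% | 23.0% | 14.9% | 5% |
| Circumference, 7 sites | reduction | 16.2% | 11.5% | 7.4% | 2.5% |
| Skin temperature, 4 sites | either | 18.5% | 15.6% | 11.4% | 5% |
| Skin temperature, 4 sites | reduction | 9.6% | 7.8% | 5.7% | 2.5% |

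A simulation of two-sided t tests with 14 per group agrees. Seven sites give 30% at r = 0, 23% at 0.5 and 11% at 0.9; four sites give 19%, 15% and 9%.

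If the tests were instead one-sided at 0.05 (replace 1.96 by 1.645 and count reductions only), the range from r = 0 to 0.8 would be 30% to 13% for circumference and 19% to 11% for skin temperature, against a nominal 5%.

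**Would the Bonferroni correction close the gap?** That depends on the family.
- Divided over the ten listed outcomes, each gets 0.05/10 = 0.005. Seven independent sites at that level give 1 − 0.995^7 = 3.5%, and 1.9% at r = 0.8. That is about four to seven times the outcome's 0.5% share.
- Divided over the sites, the levels are 0.05/7 = 0.0071 and 0.05/4 = 0.0125. These hold the error within each outcome to 5%, but the plan does not say this is intended.

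**The case against.** The strongest reply is that site-by-site testing is stated nowhere. Section 11.4.2 is just as compatible with one chosen site, an average or a sum. Its MANOVA label could mean a single omnibus test across sites, and the Bonferroni correction in the synopsis could have been meant for the sites. This stands as far as it goes: a reader might infer that uncorrected tests at every site are planned, and the documents do not support that. But neither label is tied to the sites. The synopsis describes the same analysis as a two-way repeated-measures ANOVA, and an omnibus test alone would not establish a reduction. The ambiguity is the defect.

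A reader might also multiply sites by legs and conclude that each hypothesis can be met by up to 14 tests. That is not supported either. Fourteen (7 × 2) arises only for circumference, and skin temperature cannot exceed eight (4 × 2). Both counts treat the other leg as a route to a claim about the device, whereas 11.4.3 uses side as a comparison. Seven and four are the reasonable counts, although the primary analysis never says it is limited to the operated leg.

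Two further objections are right. The hypotheses concern reductions, so the either-direction figures are about twice the chance of a false claim of benefit. And sites on one leg are unlikely to be independent, so the upper end of each range is a bound, not an expectation.

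**Conclusion.** The point holds as a gap in the definition of two of the ten primary outcomes. If operated-leg sites are tested separately at two-sided 0.05, the chance of at least one false-positive site is about 15% to 30% for circumference and 11% to 19% for skin temperature. For false reductions alone it is about 7% to 16% and 6% to 10%, or roughly three to six and two to four times the nominal 2.5%.

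These figures assume no device effect, equal correlation between sites of 0.8 to 0, and no correction across sites. The documents give no correlations. The finding does not depend on the sample size, and it does not show that a selective analysis is intended. It should be corrected, but it is narrower than the question of ten unranked primary outcomes.

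**What to change.** In 5.1 and 11.4.2, before any comparison by group is made:

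1. Define one value per outcome, on the operated leg, at postoperative day 4. For circumference this could be one named site, such as the joint-space level, or a prespecified mean of the knee-region sites. For skin temperature it could be the mean of the four sites. The choice is the investigators'; what matters is that it is fixed in advance.
2. Compare the groups on that value with adjustment for the preoperative value of the same measure.
3. Report the other sites descriptively, without p-values.
4. State in section 11 the family of tests to which the Bonferroni correction applies.
5. If the other leg is used as a covariate, use its preoperative value, because its day-4 value is measured after randomisation. No large gain in precision should be promised: baseline is already in the model, and the documents give no correlations from which to estimate what the other leg would add.

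Timing matters because 12.4 provides for monthly reports that include results and statistical analyses.

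No measurement or visit changes. The costs are that the remaining sites can no longer support a primary claim and that the plan must be amended. Redefining a primary outcome is likely to count as a substantial change, for which 2.9 requires ethics committee approval.

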#### **Range of motion [degrees]**

To estimate the range of motion of knee flexion, the "RoMot" app from OT Bioelettronica (Turin, Italy) is used. The patient is in the supine position. The two sensors are applied to the lower and thigh legs. In response to the start command, the test subject tries to bend his knee as much as possible. The heel remains in bed and the longitudinal axis of the leg is also taken into account. Then the other side is measured. The number of degrees indicated by the software on the corresponding tablet is documented. Wireless Bluetooth sensors, for determining the amount of motion, show a high correlation compared to the goniometer measurements, which are currently the most commonly used in practice (Kumar et al. 2015). The measurement moments take place preoperatively, on the 4th postoperative day and 6 weeks postoperatively.

#### **Skin temperature [°C]**

Skin temperature is also recorded with the help of an infrared thermometer (Voltcraft IR800-20D, Conrad Electronic, Hirschau, Germany). Handheld infrared thermal devices have high measurement accuracy (due to contact-free measurement) and practical handling (Stoop et al. 2020). Skin temperature is measured at four locations of the knee: superolateral, superomedial, inferolateral, and inferomedial margin of the patella (Zeng et al. 2016). The subject is in a supine position during the measurements. Both sides are measured. The measurement moments take place preoperatively, on the 4th postoperative day and 6 weeks postoperatively.

#### **Morphine consumption [number]**

The number of morphine preparations taken per day is counted and documented.

#### **Visual Analog Pain Scale [cm]**

The Visual Analog Pain Scale is documented at rest (supine position). The scale is scaled from 0 (no pain) to 10 (greatest pain imaginable) in cm increments. The test subjects are asked the following question: "How severe is your knee pain?" The measurement moments take place preoperatively, on the 4th postoperative day and 6 weeks postoperatively.

#### **10-meter walk test [sec]**

The 10-meter walking test is used because it is considered a valid and reliable measuring instrument for evaluating walking speed (Peters, Fritz, and Krotish 2013). In this assessment, the subject is asked to walk a distance of 10 meters as quickly and safely as possible. The examiner documents the time in seconds. The measurement moments take place preoperatively, on 4 weeks postoperative day and 6 weeks postoperatively.

#### **Timed-Up-and-Go [sec]**

The time-up-and-go is used because it is considered a valid and reliable measuring instrument for the evaluation of physical activity after hip and knee prostheses (Dobson et al. 2012). The subject is asked to rise from a chair while sitting and walk three meters, turn around and sit down again. The time spent on this task is measured in seconds. The measurement moments take place preoperatively, on the 4th postoperative day and 6 weeks postoperatively.

#### **Length of stay [days]**

The number of hospitalisation days (from admission to and with discharge) is counted and documented.

## **5.2 Secondary outcomes**

None available.

## **5.3 Other Outcomes of Interest**

None available.

## 5.4 Safety Outcomes

No further outcomes are included that serve safety. Discontinuation of the experiment is the responsibility of the examiners with regard to the subject's resilience. If this is estimated to be too low, the examiner can stop the experiment. If the subject does not feel well according to his or her own subjective assessment, he or she can discontinue the experiment and withdraw participation in the study. If the cold application is not justifiable for the test subject, he or she can discontinue the application. There are no disadvantages for him/her as a result. The current regulations of the Canton of Graubünden and those of the FOPH for protection against the coronavirus will be taken into account and implemented when conducting the study.

## 6. CLINICAL INVESTIGATION DESIGN

### 6.1 General clinical investigation design and justification of design

Randomized, controlled trial

It is a clinical investigation concerning medical devices (MD), Category according to Art 6 ClinO-MD (A1), whereby a CE-certified medical device is tested in the intervention group.

The group size of the participants is n=28 people (per group n=14 people). The group assignment is randomized.

### 6.2 Methods for minimising bias

All measurements are carried out and logged by the same inspector in a standardized manner. The laboratory and hospital conditions are always the same.

#### 6.2.1 Randomization

The allocation to the two different groups (Game Ready or Control group) takes place randomly when a ticket is drawn.

#### 6.2.2 Blinding procedures

Blinding the participants is not possible in this study. The examiners are blinded by the addition of another examiner who operates the apparatus. The responsible statistician is blinded and has no access to the personal data of the test persons and is not present when the data is collected.

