#### Patient satisfaction [cm]

In order to evaluate the patient satisfaction of the intervention group (Game Ready), the test subjects are asked the question "How satisfied are you with the cooling intervention?" immediately after the intervention. With the help of the Visual Analog Scale, the test subjects rate their satisfaction with a number between 0 (not at all satisfied) and 10 (maximally satisfied). The measurement moments take place twice a day (each time after the cooling intervention) during the

hospital stay.

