### 2. *Running the Test Log*

Test log	
Cooling group	Control group
Visit 1: Screening and baseline preoperatively: information, written consent, examination of /Exclusion criteria, health questionnaire Physical Function [Score] Joint circumference [mm] Range of motion [degrees] Skin temperature [°C] Visual Analog Pain Scale [cm] 10-meter walk test [sec] Timed-up-and-Go [sec]	Visit 1: Preoperative screening and baseline information, written consent, examination of /Exclusion criteria, health questionnaire Physical Function [Score] Joint circumference [mm] Range of motion [degrees] Skin temperature [°C] Visual Analog Pain Scale [cm] 10-meter walk test [sec] Timed-up-and-Go [sec]
Daily cooling intervention In addition to the usual physiotherapeutic treatment: Daily Cooling and compression. One detailed treatment description can be found in chap. 8.1.1.	Daily Control Intervention In addition to the usual physiotherapeutic Treatment: No refrigeration (see chapter 8)
Visit 4: Follow up 4th postoperative day Physical Function [Score] Joint circumference [mm] Range of motion [degrees] Skin temperature [°C] Visual Analog Pain Scale [cm] Patient satisfaction [cm] 10-meter walk test [sec] Timed-up-and-Go [sec]	Visit 4: Follow up 4th postoperative day Physical Function [Score] Joint circumference [mm] Range of motion [degrees] Skin temperature [°C] Visual Analog Pain Scale [cm] 10-meter walk test [sec] Timed-up-and-Go [sec]

Visit 5: Follow up 6 weeks postoperatively
 
Physical function [Score] Joint circumference [mm]
 
Range of motion [degrees]
 
Skin temperature [°C]
 
Visual Analog Pain Scale [cm]
	
Visit 5: Follow up 6 weeks postoperatively
 
Physical function [Score] Joint circumference [mm]
 
Range of motion [degrees]
 
Skin temperature [°C]
 
Visual Analog Pain Scale [cm]

10-meter walk test [sec]
 
Timed-up-and-Go [sec]
 
Length of stay [days]
 
Morphine consumption [number]
	
10-meter walk test [sec]
 
Timed-up-and-Go [sec]
 
Length of stay [days]
 
Morphine consumption [number]

Test log	
Rounds	Time exposure

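### As written, the plan can have the blinded assessor ask a cooling question of device patients only at the Day-4 primary endpoint; sections 5.1, 6.2, 6.2.2 and 9.1 need reconciling

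*Combined protocol and SAP*

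**What the plan says.** - **Blinding (6.2.2).** Participants cannot be blinded. For the outcome assessors the plan states: "The examiners are blinded by the addition of another examiner who operates the apparatus".
- **Who measures (6.2).** "All measurements are carried out and logged by the same inspector in a standardized manner". No outcome is exempted.
- **Time of interest (5.1).** The section declares that "the 4th postoperative day is the primary endpoint".
- **The satisfaction item (5.1, repeated in 9.2.1).** It is defined for the Game Ready arm only, and the item itself names the treatment: "How satisfied are you with the cooling intervention". It is to be rated straight after each cooling session, twice a day, during the hospital stay.
- **Day-4 list, cooling group (9.1, two-column test log).** The later items read "Visual Analog Pain Scale [cm] Patient satisfaction [cm] 10-meter walk test [sec] Timed-up-and-Go [sec".
- **Day-4 list, control group (same table).** The corresponding items read "Visual Analog Pain Scale [cm] 10-meter walk test [sec] Timed-up-and-Go [sec".
- **Second table in 9.1.** A single-column list of visit times repeats the Day-4 list with satisfaction included. It calls the visit Visit 2, where the first table calls it Visit 4.
- **Other safeguard (6.2.3).** Conversation between participant and examiner is to be kept short.

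**The concern.** Because participants know their group, blinding the assessor is the only protection the plan offers for measurements that depend on how the assessor works. Section 6.2.2 secures it by separating the person who runs the device from the person who measures. A scheduled question that names the cooling, and that only one arm is asked, would undo that separation if the measurer asks it. Keeping conversation short, as in 6.2.3, does not help, because the disclosure would come from a planned measurement and not from chance talk.

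At stake is whether the trial can be reported as assessor-blinded at its primary time point. Since section 6.2 assigns all measurements to the same person, knowledge gained on Day 4 would also carry over to the 6-week visit. The preoperative baseline would not be affected.

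**Working it through.** The plan states no figure on this point, so the check sets the sections side by side.

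1. **Compare the two Day-4 lists in the first 9.1 table.** The cooling column has 8 items: physical function, circumference, range of motion, skin temperature, pain, satisfaction, 10-metre walk and Timed-Up-and-Go. The control column has 7. The difference, 8 − 7 = 1, is satisfaction; all other items match.

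2. **Does the item identify the arm?** Section 5.1 restricts it to the Game Ready group, and its wording names the cooling. With 14 planned per group (synopsis, 6.1), it applies to 14 of 14 device patients and 0 of 14 controls. Whoever completes the full Day-4 list could therefore tell the arm of all 14 + 14 = 28 planned participants: by asking the item in one arm, and by its absence in the other.

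3. **Who completes the list?**
   - Section 6.2, read literally: the one inspector, because all measurements are that person's.
   - Section 6.2.2: outcome examiners are separate from the device operator, but no outcome is assigned to either.
   - Sections 5.1 and 9.2.1: the rating follows each session directly, when the operator is on hand, but no collector is named.
   - Section 12.2.1: the outcomes listed for the data collection form do not include satisfaction. They also omit skin temperature, so the list settles nothing.

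4. **The two possible readings.**
   - *The inspector collects satisfaction.* Sections 6.2 and 9.1 then defeat 6.2.2. If the inspector also takes the twice-daily ratings, allocation is known before Day 4.
   - *The operator collects it.* Section 6.2.2 survives, but 6.2 is too broad and the Day-4 list in 9.1 is misleading.

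   Under either reading at least one section needs correcting.

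5. **Which Day-4 outcomes are exposed under the first reading?**
   - Mainly exposed: circumference, taken by hand with a tape at seven levels on both sides, and the two timed tests.
   - Less exposed: range of motion. The assessor runs the test, but software gives the angle.
   - Little exposed: skin temperature, read from an infrared thermometer.
   - Not materially changed: KOOS and pain, which unblinded participants report themselves, the pain question having fixed wording.
   - Outside the Day-4 lists: morphine use and length of stay, which are counts.

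**The case against.** The strongest reply is that the device operator is the natural person to collect satisfaction. The only text defining the item places it immediately after each session, section 6.2.2 creates a separate operator, and section 8.3 puts a research employee at every application. Section 6.2 is a one-line statement about standardisation that does not mention satisfaction. The data collection form is an appendix that is not part of the text reviewed, so a separate sheet may exist. All of this stands as a plausible account of intended practice. None of it is written as an assignment, and the general sentence in 6.2 points the other way.

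Three stronger readings are tempting but not supported.

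- **That the assessor learns every allocation.** This needs 6.2 to be applied literally to satisfaction. No section says who asks the question.
- **That the question is put between the pain rating and the walk test.** This takes list order as testing order. The same table lists length of stay and morphine use at 6 weeks, although the first ends at discharge and the second is counted per day. A place in the list therefore fixes neither when, nor by whom, nor in what order an item is collected.
- **That an inflated false-positive rate can be quoted.** Such a figure needs an assumed shift by a knowing assessor, and the documents give no basis for one. A simple two-group calculation would also not match the group-by-time repeated-measures analysis in 11.4.2.

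It is also fair to say that assessor blinding never protected the self-reported outcomes here, so the exposure is narrower than the whole Day-4 set.

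**Conclusion.** The point holds as an internal conflict. Sections 6.2 and 9.1, followed to the letter, defeat the blinding claimed in 6.2.2 at the time point that 5.1 makes primary. If the inspector collects the item, the arm of all 28 planned participants is recognisable. If the operator collects it, blinding is not breached by this route and the fault is only in the wording. The conclusion rests on the all-measurements sentence in 6.2 covering satisfaction, which the text implies but does not state for this item.

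The outcomes at risk are chiefly circumference, the 10-metre walk and the Timed-Up-and-Go, with range of motion to a lesser degree. The size of any bias cannot be estimated from the documents. It should still be corrected, because the threat is to the plan's own safeguard and is easily removed.

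**What to change.** 1. In 5.1 and 9.2.1, state that the device operator, not the outcome assessor, collects satisfaction immediately after each session, as already timed there, on a separate form that the assessor does not see.
2. In both 9.1 tables, either take satisfaction off the assessor's Day-4 list or mark it as operator-collected. Marking it is enough if the sponsor wants this declared primary outcome to stay visible at Day 4.
3. In 6.2, limit the inspector sentence to the blinded outcome measurements.
4. In 6.2.3, add that participants are asked not to disclose their group to the assessor.

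The cost is wording changes and one separate form. The operator is already present at the sessions, so no staff are added, and the twice-daily ratings remain, so no satisfaction data are lost.
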